### 6.2.4. Sensitivity Analysis of the Secondary Efficacy Endpoints

To assess the robustness of the secondary endpoint results, the following exploratory sensitivity analyses will be performed:

## 6.3. Exploratory Efficacy Endpoints

### 6.3.1. Definition of the Exploratory Efficacy Endpoints

CCI

[Redacted]

[Redacted]

CCI

[REDACTED]

[REDACTED]

[REDACTED]

[REDACTED]

[REDACTED]

[REDACTED]

[REDACTED]

[REDACTED]

[REDACTED]

[REDACTED]

[REDACTED]

[REDACTED]

[REDACTED]

[REDACTED]

[REDACTED]

[REDACTED]

[REDACTED]

[REDACTED]

[REDACTED]

[REDACTED]

[REDACTED]

### 6.3.2. Analysis of the Exploratory Endpoints

CCI [REDACTED]

[REDACTED]

CCI

[Redacted]

[Redacted]

[Redacted]

[Redacted]

[Redacted]

[Redacted]

[Redacted]

[Redacted]

[Redacted]

[Redacted]

[Redacted]

[Redacted]

[Redacted]

[Redacted]

## **7. SAFETY ANALYSES**

Safety will be evaluated for all subjects in the Safety Analysis Set through assessment of clinical laboratory tests, physical examination findings, 12-lead ECG abnormalities, vital signs measurements, and by the documentation of AEs. Concomitant medication intake will also be recorded and coded to the corresponding WHO drug term and displayed in data listings.

All safety data collected at baseline and post-baseline through to the completion of the follow-up evaluation will be summarized. Data for the pre-treatment period will be included in data listings.

### **7.1. Adverse Events**

#### **7.1.1. Adverse Event Dictionary**

Clinical and laboratory AEs will be coded using the current version of MedDRA. System organ class (SOC), high-level group term (HLGT), high-level term (HLT), preferred term (PT), and lower-level term (LLT) will be provided in the AE dataset.

#### **7.1.2. Adverse Event Severity**

Adverse events are graded by the investigator as Grade 1, 2, 3, 4, or 5 according to the Common Terminology Criteria for Adverse Events (CTCAE) Version 4.03. The severity grade of events for which the investigator did not record severity will be categorized as “missing” for tabular summaries and data listings. The missing category will be listed last in data presentation.

#### **7.1.3. Relationship of Adverse Event to Study Treatment**

Related AEs are those for which the investigator selected “Related” on the AE case report form (CRF) to the question of related to study treatment. Relatedness will always default to the investigator’s choice, not that of the medical monitor. Events for which the investigator did not record relationships to study treatment will be considered related to study treatment for summary purposes. However, by-subject data listings will show the relationship as missing from that captured on the CRF.

#### **7.1.4. Serious Adverse Events**

Serious adverse events (SAEs) will be identified and captured as SAEs if AEs met the definitions specified in the study protocol as determined by the investigator. Serious adverse events captured and stored in the clinical database will be reconciled with the SAE database from the Gilead Drug Safety and Public Health Department before database finalization.

## **7.1.5. Treatment-Emergent Adverse Events**

### **7.1.5.1. Definition of Treatment-Emergent**

Treatment-emergent AEs (TEAEs) are events in a given study period that meet any of the following criteria:

- Any AEs with onset date of on or after andecaliximab/placebo start date and no later than 30 days after permanent discontinuation of all study treatment (andecaliximab /placebo and chemotherapy) or
- Any AEs with onset date of on or after the andecaliximab/placebo start date and no later than 55 days after permanent discontinuation of andecaliximab/placebo or
- AEs leading to discontinuation of andecaliximab/placebo

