### 7.3.1. Adverse Events

Following initiation of study medication, collect all AEs, regardless of cause or relationship, until 55 days after last administration of GS-5745/placebo or all components of mFOLFOX6, whichever is discontinued later. These must be reported to the eCRF database as instructed.

All AEs should be followed up until resolution or until the adverse event is stable, if possible. Gilead Sciences may request that certain AEs be followed beyond the protocol defined follow-up period.

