## **8.6. Safety Analysis**

All safety data collected on or after the date that GS-5745/placebo was first administered up to the date of last dose of GS-5745/placebo or mFOLFOX6 or 5-FU and LV (whichever is later) plus 55 days will be summarized by treatment group (according to the treatment received). Data for the pre-treatment and post-treatment follow-up period will be included in data listings.

In general, count and percent of subjects will summarize categorical and ordinal data. Mean, standard deviation, minimum, quartiles, median, and maximum will summarize continuous data.

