### **8.6.2. Adverse Events**

Clinical and laboratory adverse events will be coded using the Medical Dictionary for Regulatory Activities (MedDRA). System Organ Class (SOC), High-Level Group Term (HLGT), High-Level Term (HLT), Preferred Term (PT), and Lower-Level Term (LLT) will be attached to the clinical database.

Events will be summarized on the basis of the date of onset for the event. A treatment-emergent adverse event is defined as any adverse event with onset date on or after the date of first dose of study drug up to 55 days after permanent study drug discontinuation or any adverse events leading to premature study drug discontinuation.

Summaries (number and percentage of subjects) of treatment-emergent adverse events (by SOC, HLT, and PT) will be provided by treatment group.

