#### **7.2.2.1. Treatment-Emergent Laboratory Abnormalities**

Treatment-emergent laboratory abnormalities are defined as values that increase at least 1 toxicity grade from baseline at any post-baseline time point, up to 30 days after the last dose of all study treatment, or 55 days after the last dose of andecaliximab /placebo for subjects who permanently discontinued all study treatments, or all available data in the database snapshot for subjects who were still on treatment at the time of analysis. If the relevant baseline laboratory value is missing, then any abnormality of at least Grade 1 observed within the time frame specified above will be considered treatment emergent.

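### When chemotherapy outlasts andecaliximab/placebo, the SAP's treatment-emergent window closes up to 25 days before the 55-day safety-summary window in Protocol 8.3.1.2 and 8.6

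*SAP*

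**What the plan says.** The protocol uses two end points.

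- **Collection.** Protocol 7.3.1 collects AEs "until 55 days after last administration of GS-5745/placebo or all components of mFOLFOX6, whichever is discontinued later". Protocol 6.7 schedules a phone call around that time, partly to ask about AEs.
- **Summary.** Protocol 8.6 says that safety data from the first dose of study drug "up to the date of last dose of GS-5745/placebo or mFOLFOX6 or 5-FU and LV (whichever is later) plus 55 days will be summarized", with the arms shown separately. Protocol 8.3.1.2 gives the same limit for the safety analysis set.
- **TEAE definition.** Protocol 8.6.2 counts onset from first dose "up to 55 days after permanent study drug discontinuation", plus AEs that led to stopping study drug early. In Protocol 3.2, study drug means GS-5745/placebo, named apart from mFOLFOX6.

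The SAP adds its own rules.

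- The opening of SAP 7 says safety data will be summarised through the end of the follow-up evaluation.
- SAP 7.1.5.1 calls an AE treatment-emergent if it should "meet any of the following criteria": onset "no later than 30 days after permanent discontinuation of all study treatment"; onset "no later than 55 days after permanent discontinuation of andecaliximab/placebo"; or an AE that led to stopping andecaliximab/placebo.
- SAP 7.1.6 bases the AE summaries on TEAEs.
- SAP 7.2.2.1 counts treatment-emergent laboratory abnormalities "up to 30 days after the last dose of all study treatment", or to 55 days after the last andecaliximab/placebo dose. Protocol 8.6.3 counts a grade increase at any post-baseline time, with no end day of its own.
- SAP 2.4 lists one change from the protocol, the PD-L1 subgroup analysis.

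**The concern.** A subject can stop andecaliximab/placebo and stay on chemotherapy. Protocol 5.3.1.1 provides for this, after consultation with the medical monitor, when study drug is permanently stopped. The triggers it names are a Grade 3 or greater toxicity attributed to study drug that either does not resolve within 28 days or recurs after restarting. For such a subject the 55-day limit in SAP 7.1.5.1 runs from the earlier stop, and only a 30-day limit runs from the last chemotherapy dose. AEs that the protocol collects and says it will summarise can then fall outside the TEAE tables.

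Those tables are the main safety display: all TEAEs, Grade 3 or higher, serious, and leading to death. Deaths are also classified by whether they are treatment-emergent. The length of the window therefore depends on a post-randomisation event, the date of stopping study drug, and the SAP neither declares nor justifies the difference.

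**Working it through.** No sample size, power or alpha figure is involved; the check is day arithmetic.

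**Inputs**

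- A = day of the last andecaliximab/placebo dose.
- L = day of the last dose of any component.
- g = L − A. Protocol 5.3.1.1 allows g > 0. Protocol 5.3.1.2 has andecaliximab/placebo stop when all mFOLFOX6 components are permanently stopped, so g ≥ 0 under the plan.
- SAP 7.1.5.1 joins its criteria with *or*, so the later limit applies.

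**Window ends, in days after L**

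- SAP 7.1.5.1: max(L + 30, A + 55) = L + max(30, 55 − g)
- Protocol 8.6.2: A + 55 = L + 55 − g
- Protocol 7.3.1, 8.3.1.2 and 8.6: L + 55

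**Differences**

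- SAP short of Protocol 8.6: 55 − max(30, 55 − g) = min(25, g)
- SAP beyond Protocol 8.6.2: max(30, 55 − g) − (55 − g) = max(0, g − 25)

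| g (days) | SAP 7.1.5.1 end | Protocol 8.6.2 end | Protocol 8.6 end | SAP short of 8.6 | SAP beyond 8.6.2 |
|---|---|---|---|---|---|
| 0 | 55 | 55 | 55 | 0 | 0 |
| 2 | 53 | 53 | 55 | 2 | 0 |
| 14 | 41 | 41 | 55 | 14 | 0 |
| 25 | 30 | 30 | 55 | 25 | 0 |
| 28 | 30 | 27 | 55 | 25 | 3 |
| 56 | 30 | −1 | 55 | 25 | 31 |

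The row g = 2 is roughly the case where everything stops at the same visit but the end of the 46-hour 5-FU infusion is taken as the last dose. The shortfall reaches its cap of 25 of 55 days (45%) at g = 25. At g = 56 the Protocol 8.6.2 window closes one day before the last chemotherapy dose, while the SAP window runs 30 days past it.

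The third SAP criterion, AEs leading to discontinuation of andecaliximab/placebo, cannot be expected to recover these events, because they start after that drug has stopped.

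**Laboratory rule.** Read the same way, SAP 7.2.2.1 also ends at L + max(30, 55 − g). The last scheduled post-treatment safety laboratory visit is the 30-day follow-up (Protocol 6.2.8 and Appendix 2), with a ±7-day window (Protocol 6.7), so day 37 at the latest. The 55-day contact is a phone call. Since 55 − 18 = 37, a compliant 30-day sample is always counted when g ≤ 18. For larger g some late samples can be lost; for g ≥ 25 these are samples from days 31 to 37. Beyond that, only EOS visits and unscheduled tests falling after the cut-off are affected.

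**The case against.** The strongest reply concerns the comparator. A reader might infer that the SAP cuts the protocol's treatment-emergent window. It does not. The protocol's only TEAE definition is in 8.6.2, anchored on study drug, and the SAP keeps that window whole and adds 30 days after all treatment. For subjects who stay on chemotherapy longest, the SAP is the more inclusive of the two. The SAP would be narrower only if study drug in 8.6.2 meant all treatment, and the protocol's usage does not support that reading. This objection stands. Much of the trouble is a conflict inside the protocol, between 8.6 and 8.6.2, with the SAP in between.

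A reader might also infer that the events vanish. They do not: the listings of AEs, Grade 3 or higher AEs, SAEs and deaths in SAP 7.1.6.1 are not limited to TEAEs, and a late death changes category in the death summary but is still counted. That stands too.

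The loss is not general. It is zero when all drugs stop together, and Protocol 3.4 gives several reasons, including progression, for stopping study drug and all mFOLFOX6 components. The laboratory effect is small, as shown above.

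None of this removes the discrepancy. Protocol 8.3.1.2 and 8.6 and the opening of SAP 7 promise a summary that the TEAE tables do not deliver when g > 0, and SAP 2.4 is silent.

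**Conclusion.** The point holds in a limited form. When chemotherapy outlasts andecaliximab/placebo by g days, the TEAE window in SAP 7.1.5.1 ends min(25, g) days before the summary window in Protocol 8.3.1.2 and 8.6, and it also conflicts with the opening of SAP 7. The effect is omission from the TEAE tables, not loss of data. This assumes that the SAP criteria act as alternatives and that study drug means GS-5745/placebo.

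The documents do not give the share of subjects whose chemotherapy outlasts study drug, or AE rates after the last dose, so the numbers of subjects and events affected cannot be derived. A reader might assume a share of 10–30% and arrive at 43 to 129 of 430 subjects (0.10 × 430 and 0.30 × 430), but nothing in the documents supports that share. A reader might also infer bias between arms, because toxicity is one route to stopping study drug early. That is possible if early stopping differs by arm, but the documents do not show that it does.

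**What to change.** Use one analysis window in SAP 7.1.5.1, SAP 7.2.2.1 and Protocol 8.6.2: from first dose to 55 days after the last dose of andecaliximab/placebo or any mFOLFOX6 component, whichever is later. This matches Protocol 7.3.1, 8.3.1.2 and 8.6. Keep the SAP criterion for AEs leading to discontinuation of andecaliximab/placebo. List the change in SAP 2.4.

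The cost is wording in both documents and one date derivation. The AE data are already collected to that day, and no visit or treatment rule changes. The small downside is that slightly more late chemotherapy-related events will be counted as treatment-emergent.

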#### **4.2.2. Exposure to mFOLFOX6**

Exposure to individual components of mFOLFOX6 will be listed and summarized in a similar manner as for andecaliximab/placebo. mFOLFOX6 received prior to study enrollment and after the start of other anti-cancer therapy at study completion/discontinuation will not be included.

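### The treatment-emergent windows for adverse events and laboratory abnormalities do not stop when other anticancer therapy starts, so the all-cause safety tables mix in the toxicity of the next regimen

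*SAP*

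**What the plan says.** **Adverse events.** SAP 7.1.5.1 accepts an event by any of three routes: onset within 30 days of stopping all study treatment; "onset date of on or after the andecaliximab/placebo start date and no later than 55 days after permanent discontinuation of andecaliximab/placebo"; or leading to discontinuation of study drug. Protocol 8.6.2 has one day limit, "up to 55 days after permanent study drug discontinuation or any adverse events leading to premature study drug discontinuation". Neither mentions other anticancer therapy.

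**Laboratory abnormalities.** SAP 7.2.2.1 uses the same limits, "up to 30 days after the last dose of all study treatment, or 55 days after the last dose of andecaliximab" or placebo, again with no cut at new therapy.

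**Collection.** Protocol 7.3.1 tells sites to "collect all AEs, regardless of cause or relationship, until 55 days after last administration" of study drug or chemotherapy, whichever stops later. Protocol 3.4 lists progression among the reasons for ending treatment, and Protocol 1.1.1 describes second-line use of taxanes, irinotecan and ramucirumab.

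**New therapy elsewhere in the SAP.** PFS is censored for it (6.2.1.1). A response that follows it does not count (6.2.1.2). mFOLFOX6 given "after the start of other anti-cancer therapy at study completion/discontinuation will not be included" in exposure (4.2.2). Post-treatment anticancer therapies are listed only (7.6), and the concomitant-medication summary leaves out anything started after the last study-drug dose (7.4.2).

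**Attribution.** Relatedness is the investigator's choice, with missing values treated as related (SAP 7.1.3). It is summarized by drug for TEAEs, Grade 3 or higher TEAEs and SAEs (SAP 7.1.6.1).

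**The concern.** The weeks after a subject stops for progression are when a next regimen may begin. The day limits keep running through that period, so an event caused by second-line therapy is counted as treatment-emergent in the arm to which the subject was randomized. The summaries of any TEAE, Grade 3 or higher TEAEs, SAEs, TEAEs leading to death and laboratory abnormalities are then part study regimen and part something else. No described safety table shows how many subjects had moved to another regimen when the event began.

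At stake is the interpretability of the all-cause rates in both arms. A second question is whether the admixture could differ between arms. If andecaliximab delays progression, fewer of its subjects would have entered the post-treatment window by a given data cut.

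**Working it through.** **1. Reproduce the plan's PFS figure.** This is the only stated figure that bears on how far the arms would differ in progression. Inputs from SAP 1.3: control median PFS 9 months, HR 0.70, 215 per arm, 18 months' accrual plus 18 months' minimum follow-up, 10% annual dropout, one-sided 0.016, 322 events, 85% power.

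- Power with 322 events: √(322/4) × |ln 0.70| − z(0.016) = 3.200 − 2.144 = 1.056, which is 85.4%.
- Monthly hazards: control λ = ln 2/9 = 0.07702; andecaliximab 0.70 × 0.07702 = 0.05391; dropout δ = −ln(0.9)/12 = 0.00878.
- Probability of a PFS event by month 36, uniform accrual: λ/(λ+δ) × {1 − [e^(−18(λ+δ)) − e^(−36(λ+δ))] / [18(λ+δ)]}.
- Control: 0.8977 × (1 − (0.2135 − 0.0456)/1.5443) = 0.800.
- Andecaliximab: 0.8599 × (1 − (0.3235 − 0.1047)/1.1284) = 0.693.
- Expected events: 215 × (0.8001 + 0.6932) = 321.0, or 322.4 with dropout hazard 0.1/12. The stated 322 is reproduced.

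**2. Share of each arm with a PFS event.**

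| Calendar time | Control | Andecaliximab | Ratio |
|---|---|---|---|
| 12 months | 33.7% | 25.6% | 1.32 |
| 18 months | 44.0% | 34.4% | 1.28 |
| 36 months | 80.0% | 69.3% | 1.15 |
| 36 months, PFS HR = 1 | 80.0% | 80.0% | 1.00 |

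The 12- and 18-month shares are of subjects accrued by then. PFS events include deaths, so these are upper bounds for entering the window by progression. Subjects who stop for other reasons and then start new therapy are not counted here, and the documents give no rate for them.

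**3. Time under new therapy inside the window.** If second-line therapy starts 14, 28 or 42 days after the last dose, then 55 − 14 = 41, 55 − 28 = 27 or 55 − 42 = 13 days of it fall inside the 55-day limit. For the 30-day limit the figures are 16, 2 and 0.

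**4. Illustrative size at the final cut.** The documents give no second-line uptake, start time or toxicity rate, so the last two factors are assumptions: affected share = P(PFS event) × share starting therapy in the window × share of those with an event from it.

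| Assumption | Control | Andecaliximab | Difference |
|---|---|---|---|
| First Grade 3 or higher event: 30% × 10% | 2.4% | 2.1% | 0.3 points |
| First Grade 3 or higher event: 60% × 20% | 9.6% | 8.3% | 1.3 points |
| Any AE: 20% × 10% | 1.6% | 1.4% | 0.2 points |
| Any AE: 70% × 50% | 28.0% | 24.3% | 3.7 points |

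The any-AE rows overstate the effect on incidence, because a subject already counted for the same event adds nothing.

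**5. The opposing effect.** Mean follow-up before progression is P(event)/λ: 0.8001/0.07702 = 10.4 months on control and 0.6932/0.05391 = 12.9 on andecaliximab, about 2.5 months longer (an upper bound for extra treatment time). The extra post-progression window on control is (0.800 − 0.693) × 55 = about 6 days per subject.

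**The case against.** Three stronger readings are tempting, and the documents support none of them.

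- *Second-line toxicity is counted as andecaliximab toxicity.* A reader might infer this, but treatment-emergent is a timing definition. An event the investigator puts down to a second-line drug does not enter the tables of andecaliximab-related events unless relatedness is left blank. This protects only the relatedness tables. The all-cause tables ignore relatedness, and the laboratory definition has no relatedness judgement.
- *The safety tables alone run past new therapy, against a general SAP rule.* There is no such rule. OS, the primary endpoint, also continues through new therapy and is censored only at the last date known alive (SAP 6.1.1). The PFS, response and exposure rules answer other questions.
- *An excess of toxicity on andecaliximab is understated.* The net direction is not established. Under the same PFS benefit, its subjects stay on treatment longer and accumulate more on-treatment events (step 5). If it were more toxic, more of its subjects could enter the window early by stopping for adverse events.

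It is also fair to say that a fixed window is deliberately inclusive and that the listings allow affected events to be traced. With 215 per arm, the standard error of a difference in rates is √(2 × 0.5 × 0.5/215) = 4.8 points at 50% and √(2 × 0.2 × 0.8/215) = 3.9 at 20%. Both exceed every between-arm difference in step 4.

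What these points leave standing is the admixture within each arm, which needs no PFS difference and is not separated in any planned summary.

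**Conclusion.** The point holds in a limited form. As written, both documents count events that begin under another regimen as treatment-emergent in the all-cause adverse event tables, and the SAP does the same for laboratory abnormalities. That blurs both arms' rates by an amount the documents do not allow anyone to calculate. The 2.4 to 9.6 points (placebo) and 2.1 to 8.3 points (andecaliximab) for Grade 3 or higher events rest wholly on assumed uptake and toxicity.

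Bias between arms is conditional and modest. It requires a PFS difference or unequal stopping for other reasons. Under the planned PFS effect the entry ratio is about 1.15 at the final cut, and with a PFS HR of 1 progression timing creates no imbalance. Longer treatment on andecaliximab may offset it. This is a cheap improvement to the safety reporting and does not threaten the trial's conclusions.

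**What to change.** 1. In SAP 7.1.5.1 and 7.2.2.1, and in Protocol 8.6.2, summarize TEAEs, Grade 3 or higher TEAEs, SAEs and laboratory abnormalities with the window ending at the earlier of the stated day limit and the day before the first dose of other anticancer therapy. Tabulate later events separately by arm. At minimum, prespecify this as a sensitivity table beside the current window.
2. State an imputation rule for partial therapy start dates that suits this purpose. SAP 6.2.1.1 moves a missing day to the end of the month. That can place the start up to 30 days late and would keep many of the events the cut is meant to separate. The choice matters because, after the end-of-study visit, other therapy is recorded at three-monthly calls (Protocol 6.8), where partial dates are likely.
3. Reconcile the safety windows in the same edit. The SAP uses 30 days after all treatment or 55 days after study drug. Protocol 8.3.1.2 and 8.6 use 55 days after the later of study drug and chemotherapy. Protocol 8.6.2 uses 55 days after study drug.

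The cost is SAP and protocol wording, one programming condition and one extra set of tables. Therapy dates are already collected. The downside is that a delayed study-drug event beginning after new therapy moves to the separate table, so the two tables should be presented together.
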